2.4.1 Safety Determination and Criteria for Dose Modification or Interruption

National Cancer Institute Common Terminology Criteria for Adverse Events (NCI-CTCAE) version 4.03 will be used to grade the severity of toxicities. Abnormalities of laboratory tests (investigation) must be evaluated for clinical significance. Study treatment may be held, and dose may be reduced in the event of unacceptable toxicities. (see Section 2.6.8 for Guidelines.)

2.5 Selection of Study Population

2.5.1 Inclusion Criteria

Patients may be entered in the study only if they meet **all** of the following criteria:

1. Histological or cytological diagnosis of the following PTCL subtypes as defined by the WHO classification (2008) may be included:
 - a. PTCL, NOS
 - b. Angioimmunoblastic T-cell lymphoma (AITL)
 - c. Anaplastic large-cell lymphoma (ALCL), ALK⁺
 - d. Anaplastic large-cell lymphoma (ALCL), ALK⁻
 - e. Enteropathy-associated T-cell lymphoma (EATL)
 - f. Hepatosplenic T-cell lymphoma
 - g. Subcutaneous panniculitis-like T-cell lymphoma

2. Patients for whom at least 1 measurable lesion is confirmed by the lesion assessment at baseline; an evaluable lesion is defined according to Cheson Criteria 2014.
3. Relapsed or refractory disease after receiving ≥ 1 prior systemic therapy with antitumor agent(s) and there is no other standard treatment which can be considered appropriate for patients. Systemic therapy is defined as frontline chemotherapy or immunotherapy administered systemically.
4. Male or female, aged 20 years or older
5. Eastern Cooperative Oncology Group (ECOG) Performance Status of 0 to 2
6. Life expectancy of greater than 3 months
7. Meeting the following baseline laboratory criteria for screening:
 - a. Absolute Neutrophil Count $>1500/\mu\text{L}$ independent of growth factor support within 7 days
 - b. Platelets $>75,000/\mu\text{L}$ independent of transfusion within 14 days
 - c. Hemoglobin $>8 \text{ g/dL}$ independent of transfusion within 14 days
 - d. Serum creatinine $< 1.5 \times$ upper limit of normal (ULN)
 - e. Serum aspartate aminotransferase/glutamyl oxaloacetic transaminase (AST/SGOT) and alanine aminotransferase/glutamyl pyruvic transaminase (ALT/SGPT) $\leq 3 \times$ ULN
 - f. Serum Bilirubin $\leq 1.5 \times$ ULN
8. Negative serum pregnancy test for females of childbearing (reproductive) potential. Female patients of child bearing potential must use an effective method of birth control (e.g., hormonal contraceptive, intrauterine device, diaphragm with spermicide or condom with spermicide) during treatment period and 1 month thereafter. Males must use an effective method of birth control (2 barrier methods) during treatment period and 3 months thereafter.
9. Signed informed consent

2.5.2 Exclusion Criteria

Patients who meet **any** of the following criteria are **not** to be enrolled:

1. Patients in whom central nervous system lymphoma is recognized during screening (if suspected clinically, imaging study should be performed to confirm)
2. Male patients with QTcF $>450 \text{ msec}$ at screening, female patients with QTcF $>470 \text{ msec}$ at screening, or patients with congenital long QT syndrome, clinically significant arrhythmia, history of congestive heart failure (New York Heart Association Class III or IV) or acute myocardial infarction within 6 months of starting the study drug
3. Patients with known hypersensitivity to benzamide class of compounds or any of the components of HBI-8000 tablets, and patients with prior exposure of HBI-8000

4. Patients with a history of second malignancy other than disease under study. The exceptions are diseases (excluding diseases listed below) that have been treated with curative intent with no evidence of recurrence in past 5 years. Furthermore, if the second malignancy is one of the following diseases that were treated with curative intent, it is only required that there is no evidence of recurrence in past 2 years:
 - a. Basal cell carcinoma of the skin
 - b. Squamous cell carcinoma of the skin
 - c. Cervical carcinoma in situ
 - d. Carcinoma in situ of the breast
 - e. An incidental histological finding of prostate carcinoma (TNM stage T1a or T1b)
 - f. Early-stage gastric cancer treated with endoscopic mucosal resection or endoscopic submucosal dissection
 - g. Thyroid cancer with differentiated histology (e.g. papillary) treated with curative intent
5. Autologous stem cell transplantation within 12 weeks (84 days) of starting the study drug
6. History of allogeneic stem cell transplantation
7. Organ transplantation recipients except autologous hematopoietic stem cell transplantation
8. Uncontrolled inter-current infection
9. Hepatitis B surface antigen-positive, or hepatitis C virus antibody positive. In case hepatitis B core antibody and/or hepatitis B surface antibody is positive even if hepatitis B surface antigen-negative, a hepatitis B virus DNA test (real-time polymerase chain reaction measurement) should be performed and if positive, the patient should be excluded from study
10. Any history of testing positive for human immunodeficiency virus or known acquired immunodeficiency syndrome
11. Uncontrolled diabetes mellitus, hypertension, endocrine disorder, bleeding disorder
12. Major surgery or radiation therapy within 28 days of starting the study drug
13. Receiving investigational agents or anti-cancer therapy within 28 days, nitrosourea or mitomycin C within 42 days, of starting the study drug
14. Receiving antibody therapy for PTCL within 12 weeks of starting the study drug
15. Women who are breastfeeding or women who are not willing to stop breastfeeding during study treatment period and for 30 days after the last dose of study drug
16. Potential for non-compliance or at increased risk based on investigator's judgement

2.6 Study Procedures Overview

Patients may be treated in this study as long as they receive clinical benefit (stable disease or a response) in the absence of unacceptable toxicity. Disease progression would be determined by investigators based on local radiology findings and clinical judgement. No independent radiology review is required prior to designation of PD and treatment discontinuation. Independent Radiology Review and Independent Overall Efficacy Review will be performed for final efficacy analyses at the completion of this study.

To ensure patient safety, a data safety monitoring board (DSMB) will convene to review the cumulative safety profiles of study patients at following milestones: first 6 patients completing at least 1 cycle, 12, 18, 30 patients have been treated for at least 1 cycle and at end of treatment Phase of the study. Based on the observed safety, dose and regimen of ongoing treatment may be modified as needed. For all patients, weekly safety laboratory tests will be obtained during the first 28 days and closely monitored for safety signals, especially for neutropenia and transaminase elevation.

It is estimated that each patient will be on study for up to 42 months after enrollment. Assuming that 24 months are needed to meet accrual target, the study period would be of 66 months to allow efficacy and safety determination. After study drug is discontinued, patients will be followed as described in Sections 2.6.4 and 2.6.5.

Patients will be screened by the study site investigator prior to entry into the study. Patients will receive a detailed explanation of the study design, and the potential risk/benefit of treatment will be disclosed to patients prior to the screening process. Only eligible and consenting patients will be enrolled into the study. Local histopathology report could be used to consent patient. Central pathology review will be completed before efficacy analysis. The investigator will maintain a pre-screening log to record all patients prior to screening.

Similarly, local radiology reports on disease status will guide investigator's decision on study treatment, including discontinuation. At end of the study, tumor response of each patient will be reviewed by independent radiologists and oncologists in a blinded fashion to obtain best response, dates of response and progression. The data from independent and local assessment will be analyzed in parallel in final study report.

The Schedule of Events is presented in Table 4 of Appendix A (Section 9.1). The timing of PK sampling is provided in Table 5 of Appendix A.

2.6.1 Screening Assessments (within 28 days prior to start of treatment)

Written informed consent for participation in the study must be obtained before performing any study-specific screening tests or evaluations. Informed Consent Forms (ICFs) for all patients screened (whether enrolled or not) will be maintained at the study site.

All screening and baseline assessments must be completed and reviewed to confirm that patients meet all eligibility criteria. An Eligibility Screening Form (ESF) documenting the investigator's assessment of each screened patient with regard to the protocol's inclusion and exclusion criteria is to be completed and kept at the study site.

Screening assessments include medical history and concomitant medications, documentation of PTCL diagnosis in accordance with the WHO revised classification (WHO 2008) and treatment history. To consent a patient to allow screening procedure, local histology diagnosis for PTCL is acceptable. Unstained tumor pathology slides will be sent to pathology central laboratory and stained at the central laboratory. The images will be captured from the slides for central pathology review that is to be completed before efficacy analysis. For patients who do not have enough tumor tissue archived, a new biopsy will be requested. However, insufficient tumor tissue in archive or inability to perform new biopsy for any reason does not

exclude patients from entering this study. Reasonable efforts should be made to support central pathology review.

Screening assessments will be performed within 28 days prior to Cycle 1 Day 1 (C1D1). A pretreatment bone marrow test (aspiration or biopsy) would be required. Results of standard-of-care tests or examinations performed prior to obtaining informed consent and within 28 days prior to C1D1 may be used (and do not need to be repeated for screening unless they do not meet the criteria defined in the protocol). Similarly, tumor assessment tests <2 weeks outside the 28-day window in the absence of clinical evidence of PD, the results may be accepted.

Women of childbearing potential must agree to practice effective contraceptive measures after signing informed consent. A negative serum pregnancy test will be obtained during screening.

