2.10.1 Prohibited Medications and Therapy

The following drugs are prohibited.

- Drugs known to produce significant QT prolongation and ventricular dysrhythmias (see Section 9.6)

Prohibited from signing informed consent through the EoT assessment

- Anti-cancer therapy other than study medication

Prohibited during the study and within the following time intervals prior to the first dose of study drug.

- 4 weeks for anti-cancer chemotherapy
- 6 weeks for nitrosourea and mitomycin C
- 12 weeks for anti-cancer monoclonal antibody therapy

Corticosteroid prescribed for medical conditions other than lymphoma is not considered as an anti-cancer therapy for this study, for example: chronic obstructive pulmonary disease for allergy, topical steroids for rash.

Please note that patient use of any prohibited medication is considered a protocol violation. In the event of prohibited medication use, investigator should consult study medical monitor to define an appropriate course of action if needed.

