If a group of target lymph nodes becomes confluent, the PPD of the current confluent mass should be compared with the sum of the PPDs of the individual nodes, with more than 50% increase in the PPD of the confluent mass compared with the sum of individual nodes necessary to indicate progressive disease. The LDi and shortest diameter are no longer needed to determine progression.

9.4.3 **Selection of Target Lesions**

Target lesions are selected from measurable lesions, which can be nodal lesion and extranodal lesion, along with the following criteria:

- Lesions that is suitable to be measured exactly and continuously by the same method.
- Up to 6 lesions in descending order by LDi length on sectional image of CT. If measurable lesions are less than 6, all measurable lesions are selected.
- Nodes should preferably be from disparate regions of the body and should include, where applicable, mediastinal and retroperitoneal areas.

The lengths of LDi (cm) and the largest diameter (cm) which is perpendicular to LDi are measured, and their product (PPD) is the cross product of LDi and the PPD for the lesion. The sum of PPD of all target lesions (SPD) will be calculated at screening.

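### The late-scan allowance in Section 2.6.1 reaches back past the 28-day washout, so shrinkage from treatment given after the baseline scan, most plausibly radiation, can be counted as an HBI-8000 response

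*Combined protocol and SAP*

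**What the plan says.** Protocol Section 2.6.1 places screening assessments in the 28 days before Cycle 1 Day 1 (C1D1), then adds an allowance for imaging: "tumor assessment tests <2 weeks outside the 28-day window in the absence of clinical evidence of PD, the results may be accepted". Absence of clinical progression is the only condition attached.

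The washouts are set separately in Section 2.5.2:

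- Exclusion 12: "Major surgery or radiation therapy within 28 days of starting the study drug".
- Exclusion 13: "Receiving investigational agents or anti-cancer therapy within 28 days, nitrosourea or mitomycin C within 42 days, of starting the study drug".
- Exclusion 14: "Receiving antibody therapy for PTCL within 12 weeks of starting the study drug".
- Exclusion 5: "Autologous stem cell transplantation within 12 weeks (84 days) of starting the study drug".

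Section 2.10.1 repeats the general interval as "4 weeks for anti-cancer chemotherapy".

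Section 9.4.3 calculates the sum of the products of diameters (SPD) of the target lesions at screening. On choosing targets it says: "If measurable lesions are less than 6, all measurable lesions are selected". Section 9.4.9.1 measures reduction from that screening SPD, and Table 7 takes a fall of at least 50% as the target-lesion criterion for a CT-based partial response.

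**The concern.** Under the plain 28-day window the two sets of rules fit together: a baseline scan always falls inside the washout, so none of the treatments barred for 28 days can come after it. The allowance breaks that link. A standard-of-care scan can precede a course of treatment, the patient can wait the required 28 days, and the old scan still serves as baseline.

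The attached condition does not help, because it guards against growth after the scan. A patient whose disease has shrunk under other treatment passes it easily. Nothing later resets the baseline: the C1D1 assessments in Section 2.6.2 include no tumor assessment, and Table 4 schedules none between screening and Cycle 3.

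Objective response rate (ORR) is the primary endpoint of a single-arm study that Section 5.1 describes as pivotal for approval. There is no control arm in which carry-over from earlier treatment would also appear. The independent radiologists (Section 3.5.2) read the same image sequence, so their measurements start from the same baseline.

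**Working it through.** **1. The plan's own figures.** Section 5.2 gives 89% power to show ORR above 10% at two-sided 5% with N=40 and a true ORR of 30%. With X binomial, the success threshold is the smallest r for which P(X ≥ r | 40, 0.10) ≤ 0.025.

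- r = 8: 0.0419, too large.
- r = 9: 0.0155, acceptable.
- Power: P(X ≥ 9 | 40, 0.30) = 0.889, which reproduces 89%.
- Expected interval: 0.30 ± 1.96 × √(0.30 × 0.70 / 40) = 15.8% to 44.2%, also as stated.

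The sample-size figures are sound, and nothing here changes them. They imply nine responders as the threshold.

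**2. The date overlap.** Less than two weeks outside a 28-day window means at most 13 further whole days, so the oldest acceptable scan is 28 + 13 = 41 days before first dose. Exposed days = max(0, 41 − washout).

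| Prior treatment | Washout (days) | Exposed days |
|---|---|---|
| Chemotherapy and other general anti-cancer therapy | 28 | 13 |
| Radiation, major surgery | 28 | 13 |
| Nitrosourea, mitomycin C | 42 | 0 |
| Antibody therapy | 84 | 0 |
| Autologous transplant | 84 | 0 |

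The 13 days are days 41 to 29 before first dose, counted inclusively. With a strict 28-day scan window every entry is 0.

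**3. How carry-over enters the endpoint.** Reduction = (SPD at screening − SPD at evaluation) / SPD at screening × 100. If treatment after the scan has already halved the SPD by first dose, and the lesions then do not change at all on HBI-8000, the reduction is 50% and the target-lesion criterion for partial response is met.

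**4. Size per patient.** Each misattributed responder adds 1/40 = 2.5 points; an assumed 0 to 3 such patients add 0 to 7.5 points. Using the exact 95% interval that Section 5.9 prescribes:

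- 8/40 = 20.0%, interval 9.1% to 35.6%.
- 9/40 = 22.5%, interval 10.8% to 38.5%.

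**5. Sensitivity of the error rate.** The documents give no frequencies, so these inputs are assumptions: true ORR 10%, k of 40 patients treated after their baseline scan, and an added probability q of a carry-over response in each. An affected patient then responds with probability 1 − 0.9 × (1 − q), which is 0.37 for q = 0.3 and 0.55 for q = 0.5. The chance of reaching 9 responders sums over the affected and the remaining 40 − k patients.

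| k | q = 0.3 | q = 0.5 |
|---|---|---|
| 0 | 0.0155 | 0.0155 |
| 1 | 0.022 | 0.026 |
| 2 | 0.030 | 0.042 |
| 4 | 0.054 | 0.098 |

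The one-sided level implied by two-sided 5% is 0.025.

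**The case against.** The case on the other side has several parts, and much of it narrows the point.

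- **Inclusion 3.** The patient must have relapsed or refractory disease with no other appropriate standard treatment. Someone whose tumor has just halved on chemotherapy is hard to describe that way, and someone refractory to it has little shrinkage to misattribute. This makes the chemotherapy case unlikely without excluding it. Focal radiation to a measurable mass is touched much less.
- **Resected lesions.** A reader might infer that a lesion removed after the scan is a target scored as 0 × 0 mm. The first criterion in Section 9.4.3 asks for lesions suited to exact and continuous measurement by the same method, which a resected lesion does not plainly satisfy. That example should not be relied on.
- **Independent oncology review.** Section 3.5.4 gives independent oncologists the clinical data, and Section 5.9 bases the primary analysis on imaging and clinical data together. It would go too far to say that review cannot catch such a case. What stands is that no written rule tells the oncologists how to handle one.
- **Persistence.** The first scheduled response scan is by the end of week 8. Treatment ending 29 days before first dose must still show its effect about 29 + 56 = 85 days later, with no new lesions. This lowers the probability but does not remove it.
- **Generic magnitude.** The step from 8 to 9 responders applies to any single misclassification. Exactly 8/40 has probability 2.6%, 15.6% and 5.6% at a true ORR of 10%, 20% and 30%. The step shows how thin the margin is, not how often the allowance matters.
- **Timing.** Version 6.0 is dated July 2021 and planned last patient in was 3Q 2018. If accrual followed that plan, rewording Section 2.6.1 alone changes little.

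**Conclusion.** The gap is real on the text. A baseline scan up to 41 days old is acceptable, treatment with a 28-day washout can fall in the 13 days from day 41 to day 29 before first dose, and no provision requires the scan to post-date that treatment or says what to do if it does not. Post-scan radiation is the credible case.

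Three stronger readings are tempting but not supported:

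- That any prior therapy can leak through: the 42-day and 84-day washouts close the gap for their classes.
- That the reported ORR is inflated: the number of patients with an out-of-window scan, and the number treated after it, are not given, and use of the allowance is discretionary.
- That old scans bias only upward: untreated growth between an old scan and first dose counts against HBI-8000, so the net direction across all out-of-window scans is undetermined. Only the treatment-after-scan case points clearly upward.

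The shift of 2.5 points per patient is exact at N=40. The 0-to-3 range and the error rates in the last table rest on assumed frequencies. The 10% comparison takes the reference from the power statement in Section 5.2, since Section 5.1 calls the analysis primarily descriptive. The point merits correction because it is cheap to close and the primary endpoint has little slack.

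**What to change.** In Section 2.6.1, state that a tumor assessment outside the 28-day window is acceptable only if it was performed after the last prior anti-cancer therapy, radiation and major surgery, and must otherwise be repeated within the window. This brings the exposed days to zero for every treatment class in the table above. It costs one sentence and an occasional repeat scan.

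For patients already enrolled:

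- Compare each baseline scan date with the end dates of prior therapy, radiation and surgery before the independent review. Treatment history is recorded at screening, and exclusions 12 and 13 cannot be verified without those dates.
- List any patient treated after the baseline scan.
- Specify in the SAP a sensitivity ORR, with its exact 95% interval, that counts those patients as non-responders.

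The primary analysis should stay as it is. Removing lesions from the SPD or reclassifying responders there could be a major change to the primary analysis, which Section 5.1 says must also go into a protocol amendment. The sensitivity ORR may be slightly too low, because an affected patient who truly responded is counted as a failure. If the listing is empty, the check documents that the primary result is free of this bias.

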2.6.2 Baseline Assessments on Cycle 1 Day1 (C1D1)

Baseline assessments include a complete physical examination, vital signs, ECOG performance status, weight, concomitant medications, laboratory tests (hematology, chemistry, coagulation and urinalysis), and safety ECG. Women of childbearing potential must have a negative pregnancy status confirmed by serum test before dosing. If Serum pregnancy test result cannot be obtained on the same day before dosing, urine pregnancy test should be conducted additionally and the result should be confirmed before dosing (see Section 9.1). Some of the pre-dose assessments except vital signs and ECG may be performed 1 day before C1D1 to accommodate scheduling requirements in the hospital.

2.6.3 Treatment Phase

All assessments must be performed as per the Schedule of Events (see Section 9.1). Assessments scheduled on the day of study treatment should be performed prior to taking study drug, unless otherwise noted in the schedule of assessments.

Assessment of tumor response will be scheduled by end of the eighth week, then every 8 weeks (\pm 1 week) from C1D1. However, if a patient develops clinical signs and symptoms of PD, or unacceptable toxicity occurs, tumor assessment may be performed sooner as needed. For the patients with skin lesions, decision on treatment discontinuation should be based on computed tomography (CT) or positron emission tomography (PET-CT) assessment, not Modified Severity Weighted Assessment Tool (mSWAT) scores. In other words, if imaging studies showing SD or PR while mSWAT score increases, treatment will continue.

